3.5 Changes from the Protocol Planned Analysis

PPV efficacy variable (section 5.2) will be determined using adjudication panel decision rather than only using biopsy or biopsy/MRI data. This is consistent with the study objectives.

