	
 2. The rate of detection of any disease site by ¹⁸F-fluciclovine PET/CT in the study population. 3. The rate of detection of 1) prostatic bed and other pelvic disease and 2) distant metastases (i.e., bone metastases, visceral metastases, or non-regional nodal metastases) with ¹⁸F-fluciclovine PET/CT in the study population. 4. The PPV of ¹⁸F-fluciclovine PET/CT to detect regionally recurrent disease compared to biopsy in those patients who undergo a regional disease biopsy on the basis of a ¹⁸F-fluciclovine PET/CT finding or in case of bony disease a correlation with MRI or biopsy. 5. The PPV of ¹⁸F-fluciclovine PET/CT to detect distant disease compared to biopsy in those patients who undergo a distant disease biopsy on the basis of a ¹⁸F-fluciclovine PET/CT finding or in case of bony disease a correlation with MRI or biopsy. 
An independent adjudication panel will review and adjudicate ¹⁸F-fluciclovine PET/CT lesions with biopsy or MRI during follow-up to assess the PPV and, where possible, NPV, sensitivity and specificity. Rates of disease detection (radiographic only and confirmed by pathology or MRI) will be described

Safety Evaluations	Monitoring for adverse events, change in EKGs and routine hematology and biochemistry evaluations taken prior to and following receipt of ¹⁸ F-fluciclovine
Planned Interim Analyses	An interim analysis of a subset of study results on all enrolled subjects may be submitted for potential public presentation prior to completion of all data collection and analyses. As trial design will not be modified as a result of this interim analysis, no adjustment to the type I error is required.
STATISTICS Primary Analysis Plan	For the evaluation of the primary endpoint (i.e., impact on therapy), questionnaires obtained pre- and post- ¹⁸ F-fluciclovine PET/CT will be compared to calculate the fraction of cases with a change in management (versus no change in planned management). The 95% confidence interval will be calculated using the Exact method for a binomial distribution.

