1.1 Overview of Clinical Studies

Published data from single-institution studies of ^{18}F -fluciclovine PET have preliminarily demonstrated its operating characteristics in over one hundred study subjects with recurrent prostate cancer after curative-attempt primary therapy (see Figure) (5,6,7). Dosimetry has previously been described and is notable for a favorable pelvic imaging profile because of low levels of uptake within the urinary bladder. ^{18}F -fluciclovine PET/CT has demonstrated approximately 90% sensitivity and 40-67% specificity for detection of cancer in the prostate bed. It has demonstrated 55-100% sensitivity and more than 95% specificity for the detection of disease outside of the prostate bed. Multi-center study is needed to determine the clinical impact of localization of suspected prostate cancer recurrence by ^{18}F -fluciclovine PET/CT, specifically the impact on patient management.

The goal of the proposed study is to further evaluate the impact of ¹⁸F-fluciclovine PET/CT of prostate cancer in a multi-institution study. We hypothesize that by identifying disease in or outside of the prostate bed—either in regional lymph nodes or distant disease sites, ¹⁸F-fluciclovine PET/CT will impact the approach to patient management. This typically involves prostate bed irradiation in patients with prior prostatectomy, and a combination of additional focal therapy such as radiotherapy, cryotherapy, and/or systemic therapy in patients treated initially with local radiotherapy or brachytherapy. We propose a study of men who have undergone definitive treatment of localized prostate cancer (e.g. by prostatectomy, local radiotherapy, brachytherapy) and are presenting with rising PSA levels indicative of recurrent or persistent disease. We have chosen to study patients without evidence of disease (or with equivocal findings) by standard imaging (bone scintigraphy and CT or MRI) and with PSA levels in the range where imaging findings outside the prostatic bed would be expected to have a significant impact on treatment. Study participants with negative or equivocal conventional staging studies (^{99m}Tc-MDP bone scintigraphy /NaF PET-CT (dependent on standard of care at the institution) and abdominal-pelvic CT or MRI) will undergo ¹⁸F-fluciclovine PET/CT.

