3.2 Secondary Objectives

1. To measure the fraction of patients for whom ^{18}F -fluciclovine PET/CT leads to a change of actual management by comparison with the intended management plan before ^{18}F -fluciclovine PET/CT.
2. To estimate the fraction of patients in whom ^{18}F -fluciclovine PET/CT yields evidence of recurrent disease on the basis of imaging results.
3. To estimate 1) the rates of detecting regionally recurrent disease (i.e., prostatic bed-only and/or pelvic disease outside of the bed) and 2) the rate of detecting distant metastases (i.e., bone metastases, visceral metastases, or non-regional nodal metastases) with ^{18}F -fluciclovine PET/CT in the study population.
4. To determine 1) the PPV of ^{18}F -fluciclovine PET/CT to detect regionally recurrent disease and 2) the PPV of ^{18}F -fluciclovine PET/CT to detect distant metastases in the study population in patients who undergo optional biopsy of ^{18}F -fluciclovine PET/CT findings or have documentation of disease status based on other imaging and/or follow-up data. For soft tissue disease these calculations will be limited to those patients who undergo a confirmatory biopsy and for bone disease those with confirmatory findings on MRI any time during the 6-month follow up. The denominator for the analysis will be [lesions biopsied + bone lesions].
5. To explore differences in estimated cost of treatment plans determined prior to and following ^{18}F -fluciclovine PET/CT.

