5.2 Secondary Efficacy Endpoints

1. Per-patient impact (yes/no) of ^{18}F -fluciclovine PET/CT on pre-PET intended versus post-PET actual patient management (assessed at 6 months post scan)

2. The rate of detection of any disease site by ^{18}F -fluciclovine PET/CT in the study population;
3. The rate of detection of 1) prostatic bed and other pelvic disease and 2) distant metastases (i.e., bone metastases, visceral metastases, or non-regional nodal metastases) with ^{18}F -fluciclovine PET/CT in the study population;
4. The PPV of ^{18}F -fluciclovine PET/CT to detect regionally recurrent disease compared to biopsy in those patients who undergo a regional disease biopsy on the basis of a ^{18}F -fluciclovine PET/CT finding or in case of bony disease a correlation with MRI or biopsy.
5. The PPV of ^{18}F -fluciclovine PET/CT to detect distant disease compared to biopsy in those patients who undergo a distant disease biopsy on the basis of a ^{18}F -fluciclovine PET/CT finding or in case of bony disease a correlation with MRI or biopsy.

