14.2 Analysis of Secondary Endpoints

For the evaluation of the secondary endpoint examining actual impact on therapy, questionnaires obtained pre-FACBC will be compared to treatment executed post-¹⁸F-fluciclovine PET/CT to calculate the fraction of cases with a change in management (versus no change in planned management). For the estimation of detection rate, the proportion of the ¹⁸F-fluciclovine -PET/CT positive results, 95% confidence interval will be calculated using the Exact method for a binomial distribution.

For each patient a comparison will be made of the results of the ¹⁸F-fluciclovine PET/CT results, any histopathology results, results of any other imaging and also for the clinical response to treatment(s) (standard of truth) by an Adjudication Panel. The PPV, NPV, sensitivity and specificity will be calculated, where possible, at lesion or regional or patient level. The PPV will be calculated separately for patients undergoing optional biopsy for (1) regional disease and (2) distant disease. The 95% confidence interval will be calculated using the Exact method for a binomial distribution. The Adjudication Panel will follow the Adjudication Manual that will prospectively document the processes to be used to determine a decision concerning the result of the ¹⁸F-fluciclovine PET/CT scan vs standard of truth.

Rates of disease detection (radiographic only and confirmed by pathology or MRI) will be described

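### The SAP tabulates PPV only against the adjudication panel, so the biopsy/MRI-verified PPV planned in the protocol is lost and any inflation of the panel PPV could not be seen

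*SAP*

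**What the plan says.** **Protocol, endpoints and analysis.** In 5.2, endpoint 4 sets the PPV for regional disease "compared to biopsy in those patients who undergo a regional disease biopsy on the basis of a" PET/CT finding; bone may be checked by MRI or biopsy. Endpoint 5 does the same for distant disease. Section 14.2 adds: "The PPV will be calculated separately for patients undergoing optional biopsy for (1) regional disease and (2) distant disease".

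**Protocol, objective 4 (3.2).** The objective first admits patients whose disease status is documented by other imaging or follow-up. It then narrows the calculation: "For soft tissue disease these calculations will be limited to those patients who undergo a confirmatory biopsy", with MRI confirmation for bone.

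**Protocol, the panel.** The synopsis has an independent panel adjudicate PET/CT "lesions with biopsy or MRI during follow-up to assess the PPV and, where possible, NPV, sensitivity and specificity". In 14.2 the panel sets the PET/CT result beside "any histopathology results, results of any other imaging and also for the clinical response to treatment(s) (standard of truth) by an Adjudication Panel".

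**SAP.** Section 3.5 declares that the PPV variable "will be determined using adjudication panel decision rather than only using biopsy or biopsy/MRI data" and calls this consistent with the objectives. Section 5.2 lists both PPVs against the panel decision. Section 5.4.2.2 names that decision as the reference and promises a count of indeterminate responses. Scan results, other imaging and adjudication decisions are listed. No table gives a PPV restricted to biopsied or MRI-checked findings, and none breaks the panel PPV down by the evidence behind it.

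**The concern.** Two things are at stake.

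The first is a lost analysis. The protocol planned a PPV whose truth came from tissue, or from MRI or biopsy for bone. Under the SAP a reader gets one panel PPV per region and cannot tell how many of its true positives were verified and how many inferred. Biopsy is optional (Protocol 9.2, item 9), so the inferred share could be large.

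The second is possible incorporation of the index test into its own reference. The panel has the PET/CT result before it, and neither document says that truth is fixed blind to it. Treatment response is part of the evidence, and treatment can follow from the scan: the revised plans in SAP 5.4.1 include boosts and resections guided by fluciclovine. SAP 5.4.2.4 measures response by PSA, a serum level that does not show where disease lies, yet the PPV is claimed by region. If a response after PET-guided treatment were taken to confirm the PET site, the panel PPV would lean towards the scan.

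**Working it through.** The documents give no expected PPV and no target precision for it, and the sample size rests on the primary endpoint. There is no plan figure to reproduce, so the textual comparison comes first and then an illustration.

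**1. The passages compared.**

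| Item | Protocol | SAP |
|---|---|---|
| Reference for PPV | Biopsy; MRI or biopsy for bone (5.2) | Panel decision (3.5, 5.2, 5.4.2.2) |
| Who enters, soft tissue | Biopsied patients (3.2, 14.2) | FAS, repeated on PPS (5.4.2.2) |
| Panel evidence | Histopathology, other imaging, treatment response (14.2) | Left to the Adjudication Manual (5.4.2.2) |
| Truth set blind to PET? | Not stated | Not stated |
| Verified PPV tabulated? | Yes (14.2) | No |

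SAP 3.1 repeats objective 4 without the sentence in Protocol 3.2 that limits the calculation. The claim of consistency in SAP 3.5 is therefore partly right: it fits the opening of the objective but not its restriction.

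**2. Inputs for the illustration.** Protocol 1.1 gives "approximately 90% sensitivity and 40-67% specificity for detection of cancer in the prostate bed". Assumed, because the documents do not give them: bed prevalence 0.5 (range 0.3 to 0.7), 30% of positives biopsied, and 90-100% of the rest called true positive by the panel (*c*).

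**3. PPV under an independent reference.** *p* = 0.9π / [0.9π + (1 − spec)(1 − π)]. At π = 0.5:
- specificity 0.40: 0.45 / (0.45 + 0.30) = 0.60
- specificity 0.67: 0.45 / (0.45 + 0.165) = 0.732

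**4. Panel PPV.** 0.3*p* + 0.7*c*, so the gap is 0.7(*c* − *p*).
- specificity 0.40: 0.18 + 0.63 = 0.81 to 0.18 + 0.70 = 0.88; gap 21 to 28 points
- specificity 0.67: 0.22 + 0.63 = 0.85 to 0.22 + 0.70 = 0.92; gap about 12 to 19 points
- if truth is set independently of PET, *c* = *p* and the gap is zero

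**5. Sensitivity to prevalence.** At π = 0.3 and specificity 0.40, *p* = 0.27/0.69 = 0.391 and the gap is 0.7 × 0.509 = 36 to 0.7 × 0.609 = 43 points. At π = 0.7 and specificity 0.67, *p* = 0.63/0.729 = 0.864 and the gap is 0.7 × 0.036 = 3 to 0.7 × 0.136 = 10 points.

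**6. A second model, same direction.** Let the panel take the PET result as truth in a share *w* of positives, so that panel PPV = *p* + (1 − *p*)*w*. With *p* = 0.60, this gives 0.70, 0.80 and 0.90 at *w* = 0.25, 0.50 and 0.75, and 0.60 at *w* = 0.

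**7. Outside the bed.** Protocol 1.1 gives sensitivity 55-100% and specificity above 95%. Taking specificity 0.95 and π = 0.5, *p* runs from 0.275/0.300 = 0.917 to 0.500/0.525 = 0.952. The gap in step 4 is then 0.7(0.90 − 0.952) = −4 to 0.7(1.00 − 0.917) = +6 points. Lower prevalence would increase it. These figures pool pelvic nodes with distant sites, so they do not estimate the effect for distant disease.

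**8. Precision of a verified PPV.** With an assumed 30 verified positives and 18 confirmed (0.60), the exact 95% CI is 0.41 to 0.77. With 12 of 20 it is 0.36 to 0.81, and with 27 of 45 it is 0.44 to 0.74.

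**The case against.** The sponsor has good answers to any stronger reading.

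- A reader might infer that histology has been discarded. The SAP moves away from using biopsy or MRI data alone; both remain available to the panel. The change is declared, and Protocol 14 lets the SAP modify the analysis.
- A reader might infer that the SAP brought in the panel and treatment response. Both are in the protocol already (synopsis and 14.2).
- A reader might infer that the change contradicts the objectives. Objective 4 does admit other imaging and follow-up data, and the synopsis version carries no biopsy restriction.
- A reader might infer that bias is established. The Adjudication Manual governs how truth is set and is not among the documents; it may require blinding. Nothing says that a PSA fall confirms a site, since SAP 5.4.2.4 is a separate response analysis. Indeterminate decisions are reported, so unverified cases need not be scored true positive.
- A biopsy-only PPV is not a clean benchmark. Protocol 9.2 directs biopsy to soft-tissue findings with anatomical support, where it is feasible and safe, which may select likelier true positives.

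All of this stands. It limits the point to a lost analysis and an unquantified risk. It does not restore the verified PPV or show the reader which positives were verified.

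**Conclusion.** The point holds in this form. The protocol planned a PPV verified by biopsy, or by MRI or biopsy for bone. The SAP widens the reference to the panel decision, tabulates no verified PPV, and describes as consistent with the objectives a change that is only partly so. The panel PPV may be inflated, because blinding to PET is not stated and treatment response can follow from PET-guided treatment without localising disease.

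The documents do not show that inflation occurs, and its size is unknown. The 21-28 and 12-19 point gaps illustrate the prostate bed only. They depend on the assumed prevalence, biopsied share and panel behaviour, the last of which builds in the effect. They should not be read as estimates, nor carried over to distant disease.

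PPV is a secondary endpoint. The primary endpoint and the sample size are unaffected. The change should be made because it is cheap and the gap cannot be closed from the planned tables.

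**What to change.** Keep the panel PPV as the SAP has it, and make two additions to SAP 5.4.2.2.

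1. **A named supportive analysis.** Report the biopsy-verified PPV (MRI or biopsy for bone) for regional and for distant disease, with exact 95% CIs. The denominator is all PET-positive findings that had a biopsy, or MRI for bone, whatever the result. This wording matters: if the confirmatory language in Protocol 3.2 were read as admitting only confirmed findings, PPV would be 100% by construction. State the unit as well, since Protocol 3.2 counts lesions while SAP 5.4.2.2 gives one outcome per subject and region.
2. **Panel PPV by source of truth.** Tabulate it as histology, MRI or other imaging, and treatment response or follow-up only.

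In the same section, state whether the panel sets truth blind to PET/CT and how a case with neither biopsy nor MRI is classified. SAP 3.5 should say that the separate PPV in biopsied patients is now supportive.

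The cost is two tables. Biopsy and restaging results are already abstracted (Protocol 10.6); the source of truth has to be taken from the adjudication data. The verified PPV will have a small denominator, a wide interval and selected cases, so it belongs beside the panel PPV and should not be presented as an unbiased benchmark.

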4 STUDY SUBJECTS

4.1 Analysis sets

The list of subjects to be included in each of the analysis sets is to be agreed between the Syne qua non statistician and Blue Earth Diagnostics once all study data are available and prior to database lock.

Enrolled Set: All subjects who entered screening.

Safety Analysis Set (SAF): All subjects who have been included in the database and have been administered ^{18}F -fluciclovine will be included in the Safety Analysis Set (SAF).

Full Analysis Set (FAS): All subjects enrolled who have had an ^{18}F -fluciclovine PET/CT scan will be included in the Full Analysis Set (FAS).

Evaluable Analysis Set (EAS): All subjects from the FAS who have an intended treatment management plan completed and a revised management plan page completed will be included in the Evaluable Analysis Set (EAS).

Per Protocol Set (PPS): All subjects in the EAS who meet the second and third protocol inclusion criteria (see protocol section 6.2) and any other subject without major significant deviation following review of the protocol deviation list.

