5.4 Statistical Analysis

5.4.1 Primary Efficacy Analysis

The primary efficacy analysis will be based on the EAS and will be repeated on the PPS as a secondary analysis. Comparisons between the original treatment plan and the revised treatment plan will be categorised as no change, major change or other change. The definitions of the change categories are listed below.

- No change: the original treatment plan is the same as the revised treatment plan
- Major change: the original treatment plan is not the same as the revised treatment plan and the grouping for the original treatment plan is not the same as the grouping for the revised treatment plan

These will be further split and presented according to the following categories:

- Salvage or Non-curative systemic therapy to Watchful waiting
 - Salvage therapy to Non-curative systemic therapy
 - Non-curative systemic therapy to Salvage therapy
 - Alternative Major change
- Other change: the original treatment plan is not the same as the revised treatment plan but the grouping for the original treatment plan is the same as the grouping for the revised treatment plan

These will be further split and presented according to the following categories:

- Modified RT field plan
- Modified androgen-deprivation regimen
- Alternative Other change

Groupings of treatment plans are detailed in the following table:

Original Treatment Plan	Grouping for Original Tx Plan	Revised Treatment Plan	Grouping for Revised Tx Plan
Was androgen deprivation therapy planned	Androgen Deprivation Therapy	Androgen deprivation therapy	Androgen deprivation therapy
		Active surveillance	Active surveillance
		Chemotherapy	Chemotherapy
Salvage radiotherapy to the prostate bed	Salvage Radiotherapy	Salvage radiotherapy to the prostate bed	Salvage Radiotherapy
Salvage radiotherapy to the prostate bed, with boost to areas guided by conventional imaging		Salvage radiotherapy to the prostate bed, with boost to areas guided by conventional imaging	
		Salvage radiotherapy to the prostate bed with boost to areas guided by fluciclovine (18F) PET/CT	
Salvage radiotherapy to the prostate bed and whole pelvis	Salvage Radiotherapy	Salvage radiotherapy to the prostate bed and whole pelvis	Salvage Radiotherapy

Original Treatment Plan	Grouping for Original Tx Plan	Revised Treatment Plan	Grouping for Revised Tx Plan

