5.4.2.2 Diagnostic performance of ¹⁸F-fluciclovine

Diagnostic performance will be assessed by calculating sensitivity, specificity, Positive Predictive Value (PPV), and Negative Predictive Value (NPV), using subject based analyses. Further calculations will be made for intra-prostatic / prostate bed and extra-prostatic disease. Reference tests will be the adjudication panel decision. The Adjudication Panel will follow the Adjudication Manual that prospectively documents the processes to be used to determine a decision concerning the result of the ¹⁸F-fluciclovine PET/CT scan vs standard of truth. The number and percentage of indeterminate responses will be reported.

The sensitivity, specificity, PPV and NPV will be calculated as:

- Sensitivity = $TP / (TP + FN)$
- Specificity = $TN / (FP + TN)$
- PPV = $TP / (TP + FP)$
- NPV = $TN / (FN + TN)$

where TP, TN, FP and FN refer to true positive, true negative, false positive and false negative results respectively.

Definitions of these summaries will be based on the table below.

		Reference tests		
		Positive	Negative	
Fluciclovine (¹⁸ F) scan results	Positive	True Positive (TP)	False Positive (FP)	TP+FP
	Negative	False Negative (FN)	True Negative (TN)	FN+TN
		TP+FN	FP+TN	n

The number, percentage and exact 95% CIs of TP, FP, FN and TN, as well as the point estimates (expressed in percentages) and their associated exact 95% CIs, of the Sensitivity, Specificity, PPV and NPV, will be presented at the subject level and the region level for the FAS, where the region level estimates will be calculated separately for each region: prostatic region and extra-prostatic region. The region level results will be derived at the subject level for each region resulting in one outcome for each subject in each region. For the subject level analysis, if a subject has at least one positive result, the subject will be categorised as positive. If all of a subject's results are negative the subject will be categorised as negative. For the region level analysis, if a subject has at least one positive result from the prostatic region the subject will be categorised as positive for the prostatic region. If all results related to the prostatic region are negative for a subject, that subject will be categorised as negative for the prostatic region. Similar classification rules apply for the extra-prostatic region.

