Note that the subgroup analyses will only be performed if there are sufficient data for these analyses to be meaningful.

These estimates will be repeated separately for regionally recurrent disease (prostate/prostate bed), pelvic lymph nodes and distant metastases (retroperitoneal lymph nodes, other lymph nodes, soft tissue/parenchyma and bones), a summary for lymph nodes (overall) will also be presented. Once again the region level results will be derived at the subject level and subjects will be categorised as positive or negative for each region in a similar manner to that described above for the prostatic region.

These subject and location level summaries will be repeated by the following baseline PSA subgroups:

- 0 – 0.2
- >0.2 – 0.5
- >0.5 – 1.0
- >1.0 – 2.0
- 2.0 – 5.0
- 5.0 – 10.0
- >10.0

and across the following baseline Gleason score categories: ≤ 6 , 7, 8 and ≥ 9 . All these summarise will be repeated for the PPS.

All ^{18}F -fluciclovine PET/CT results, other imaging results and adjudication decision data will be listed.

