5.4.2.3 Detection rates

The detection rate (DR) will be calculated as $(\text{TP}+\text{FP})/n$ from the above table.

The point estimate (expressed in percentage) of the DR will be presented at the region level and at the subject level, as well as for the prostatic bed, other pelvic disease and distant metastases. These rates will be presented for all subjects from the FAS and PPS, overall and across a range of baseline PSA values:

- 0 – 0.2
- >0.2 – 0.5
- >0.5 – 1.0
- >1.0 – 2.0
- 2.0 – 5.0
- 5.0 – 10.0
- >10.0

to determine the optimum PSA threshold for lesion detection.

The detection rates will also be summarised across the following baseline Gleason score categories: ≤ 6 , 7, 8 and ≥ 9 .

All detection rate data will be listed.

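### The Per Protocol Set requires both management-plan forms, so eligible men with a valid scan but a missing form drop out of the per-protocol repeat of detection rate and diagnostic performance

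*SAP*

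**What the plan says.** SAP 4.1 defines nested sets. The FAS is every enrolled subject who had the scan. The EAS is "All subjects from the FAS who have an intended treatment management plan completed and a revised management plan page completed". The PPS is "All subjects in the EAS who meet the second and third protocol inclusion criteria", that is, the PSA criterion and the negative-or-equivocal conventional imaging criterion of Protocol 6.2. The PPS definition then continues "and any other subject without major significant deviation following review of the protocol deviation list".

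The sets are used as follows:

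- Change in management (SAP 5.4.1): "The primary efficacy analysis will be based on the EAS and will be repeated on the PPS as a secondary analysis".
- Sensitivity, specificity, PPV and NPV (SAP 5.4.2.2): these "will be presented at the subject level and the region level for the FAS", and then "All these summarise will be repeated for the PPS".
- Detection rate (SAP 5.4.2.3): "These rates will be presented for all subjects from the FAS and PPS".

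SAP 5.4.2.2 takes the adjudication panel decision as the reference test. SAP 5.4.2.3 defines detection rate as scan-positives, true and false, over the table total. Neither definition uses a management-plan questionnaire. SAP 2 and 5.4.3 rule out imputation, and no separate per-protocol set is defined for the imaging endpoints.

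**The concern.** The EAS condition is right for an endpoint that compares two plan forms. Carried through the PPS into the imaging endpoints, it removes men for a reason that has nothing to do with how they were selected or scanned, or with how their disease status was adjudicated.

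The revised form is completed after the scan, so its completion can depend on the result. Protocol 9.2 (item 8) asks that any further imaging or biopsy prompted by the PET/CT be considered before the revised plan is recorded. Protocol 10.5 schedules that form 2 to 22 days after the scan, while Protocol 9.2 (item 9) accepts biopsies up to 4 months after imaging. Men whose scans lead to further work-up are therefore the ones whose revised form is most likely to be late. A late form may still count, since SAP 4.1 sets no time limit, so loss is possible rather than certain.

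Protocol 10.8 also keeps a withdrawn subject's data in the analysis if the baseline measures are complete. A man who withdraws after the scan and before the revised form stays in the FAS but leaves the PPS imaging results.

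At stake is whether a difference between the FAS and PPS imaging results can be put down to eligibility and deviations, or partly reflects who had a form returned.

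**Working it through.** **1. What each outcome needs, against what the PPS requires**

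| Outcome | Data needed | Both forms needed? | Form-conditioned PPS suitable? |
|---|---|---|---|
| Change in management (5.4.1) | both plan forms | yes | yes |
| Detection rate (5.4.2.3) | scan result | no | no |
| Sensitivity, specificity, PPV, NPV (5.4.2.2) | scan result and adjudication decision | no | no |

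If the detection-rate denominator is limited to adjudicated subjects, because it is read from the 5.4.2.2 table, the form is still not needed.

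**2. The last clause of the PPS definition**

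- Read as a further restriction within the EAS: the PPS repeat of 5.4.1 works, and the imaging repeat loses men without forms.
- Read as adding men from outside the EAS: the imaging repeat regains them, but the PPS repeat of 5.4.1 then contains men whose change of plan cannot be classified.

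The first reading is the natural one, because 5.4.1 needs both forms. On either reading one of the two uses fails.

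**3. The plan's own figures (Protocol 14.4, SAP 3.4)**

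- Exact 95% interval at 30% with n = 89: 0.207 to 0.406, width 0.199, as tabulated.
- 89 / 0.40 = 222.5, rounded up to 223.
- With 248 men, the probability of at least 89 positives at 40% is 0.918, which meets the stated 90%.
- 248 / (1 − 0.15) = 291.8, rounded up to 292.

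These reproduce and are not in dispute. They supply the inputs below.

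**4. Size of a possible shift in the PPS detection rate**

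Inputs: FAS positivity p = 0.40 (Protocol 14.4). The share m of scanned men lacking a form is not given; 0 to 15% is assumed, with the whole planned data loss as the upper end. The share s of those men who are scan-positive is unknown and runs from 0 to 1. All 292 are taken as scanned, and no one is excluded for any other reason.

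PPS detection rate = (p − s·m) / (1 − m)

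| m | all missing scan-positive (s = 1) | unrelated to result (s = 0.40) | all missing scan-negative (s = 0) |
|---|---|---|---|
| 5% | 0.35/0.95 = 36.8% | 40.0% | 0.40/0.95 = 42.1% |
| 10% | 0.30/0.90 = 33.3% | 40.0% | 0.40/0.90 = 44.4% |
| 15% | 0.25/0.85 = 29.4% | 40.0% | 0.40/0.85 = 47.1% |

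In whole men at 15%: 117 of 292 positive (40.1%) and 44 forms missing, giving 73/248 = 29.4% or 117/248 = 47.2%.

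**5. Precision**

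The exact 95% interval (Protocol 14.2) for a 40% rate has width 0.115 with 292 men and 0.125 with 248. The loss of precision is small. The most extreme shift at 5% missing (3.2 points) is below the half-width with 277 men (0.119/2, about 6.0 points). At 15% missing, both extremes (10.6 points down, 7.1 up) exceed the half-width with 248 men (0.125/2, about 6.3 points).

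**6. Diagnostic performance**

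If form completion depends only on the scan result, PPV and NPV are not shifted, but sensitivity and specificity are. If it also depends on work-up that tracks true disease status, all four can shift. The documents give no figures from which to size this.

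**The case against.** The strongest reply is that this touches only a repeat analysis. The FAS results for both imaging endpoints are reported and lose no scan, Protocol 14.2 asks for no per-protocol imaging analysis, and the primary analysis is on the EAS. All of that stands. A reader might infer that valid scans disappear from the trial's imaging results, or that the primary result is compromised; neither follows.

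Second, the last clause of the PPS definition might readmit compliant men without forms. The wording allows that, but the reading breaks the PPS repeat of 5.4.1, so it moves the fault without removing it.

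Third, the forms are themselves protocol procedures. Protocol 10.2 requires the pre-scan questionnaire and Protocol 10.3 checks it before dosing, so a single per-protocol set that demands them is arguable. The documents also nowhere state what the FAS-to-PPS comparison is for. But a missing form does not invalidate a scan or an adjudicated status, and the SAP does not class it as a major significant deviation. It is fair to add that a missing intended form precedes the scan and cannot be caused by its result, so the bias argument rests on the revised form.

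Fourth, a reader might infer that any FAS-to-PPS difference would be uninterpretable. That is too strong. SAP 4.2 lists each subject's EAS membership with the reason for exclusion, and 5.4.2.2 and 5.4.2.3 list scan and detection data, so the difference can be partly traced.

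Fifth, the 15% in Protocol 14.4 is a general allowance for data loss, not a missing-form rate. Scans that were never done leave the FAS too and create no contrast. The 29.4% to 47.2% range also needs every missing form to fall in one scan-result group. It is a bound and should not be read as an expected effect.

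**Conclusion.** The concern holds as a defect in the PPS definition as used for the imaging endpoints. On the natural reading of SAP 4.1, the per-protocol repeat of detection rate and diagnostic performance is conditioned on completion of forms that those outcomes do not use. The repeat is biased only if form completion is related to the scan result or, for performance, to true disease status. The protocol's sequence of work-up before the revised plan makes such a link plausible but does not establish it.

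On the assumptions above, the PPS detection rate would lie within 36.8% to 42.1% against a true 40% at 5% missing, and within 29.4% to 47.2% at 15%, the latter being an upper bound. The actual missing-form rate, and so the actual effect, cannot be learned from the documents. Because the FAS imaging results and the primary analysis are untouched, this is a point the sponsor should correct, not one that threatens the trial's main conclusions.

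**What to change.** In SAP 4.1, add an imaging per-protocol set: FAS subjects who meet inclusion criteria 2 and 3 of Protocol 6.2 and have no major significant deviation, with no requirement for either management-plan form. Use it in place of the PPS in 5.4.2.2 and 5.4.2.3.

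Keep the EAS-based PPS for 5.4.1, and reword its last clause so that freedom from major significant deviation is a further restriction within the EAS, not a route into the set from outside.

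The cost is one definition and one population flag, with no new data. SAP 1 has the plan finalised before database lock, so the change can be made then. The small downside is that the two per-protocol sets will have different denominators, which the table titles should make plain.
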